### 9.4. Statistical Analyses

The SAP will be developed and finalized before database lock and will describe the participant populations to be included in the analyses, and procedures for accounting for missing, unused, and spurious data. This section is a summary of the planned statistical analyses of the primary and secondary endpoints.

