## 4. ANALYSIS SETS (POPULATIONS FOR ANALYSIS)

Data for all participants will be assessed to determine if participants meet the criteria for inclusion in each analysis population prior to releasing the database and classifications will be documented per standard operating procedures.

All subjects at site **CCI** will be excluded from all the analysis populations due to violation of GCP principles (i.e., suspected falsification of study records).

Population	Description
Enrolled Population	All participants who are enrolled in TP1. This population will be used for participant accountability in TP1.
Safety Population for TP1 (Safety-TP1)	All participants who are enrolled in TP1 and receive at least one dose of investigational product in TP1. This population will be used for the TP1 safety analyses.
Intent-to-Treat Population (ITT-Randomized)	All participants who are randomized to a study treatment group at Study Week 10. This population will be used for participant accountability during TP2 through TP4.
Safety Population (Safety-Randomized)	All participants who are randomized and receive at least one dose of investigational product following the randomization at Study Week 10. The Safety Population will be used for the safety analyses during TP2 and beyond, ADA and NAb analyses and the secondary PK endpoint ( $C_{\text{trough}}$ ).
PK population	All randomized participants who are dosed to initiate the Week 30 steady-state PK profile, remain on background MTX with no major protocol deviations influencing the PK assessment, such as a miss dose (the first dose of the study in TP1 cannot be missed, no more than 1 missed dose allowed per TP except Week 32 dose, no more than 2 missed doses allowed in TP1 through TP4 except Week 32 dose, participants can only miss or have an incomplete dose for either the first or second dose in TP4 (but not both), and the study doses on Weeks 26, 28, and 30 cannot be missed or incomplete), and have at least 1 primary endpoint ( $AUC_{\tau}$ or $C_{\text{max}}$ ). The last study dose in TP4 on week 32 after the PK assessments is not included in the definition of the population for analyses and can be missed or be incomplete. Subjects will be excluded from the PK population in case of missed PK sample(s) which significantly affect the calculation of PK parameters. The PK population will be used for the primary PK analysis and other secondary PK endpoint analyses ( $T_{\text{max}}$ , $C_{\text{av}}$ , and CL/F).

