The determination of PK population independent of the PK test results will be finalized prior to the releasing of the study database.

Protocol deviations independent of PK test results will be determined on an ongoing basis per data review. Any participant with major protocol deviations that affect PK assessment as determined by the study team will be excluded from the PK population. Major protocol deviations may include: Missing or incomplete dosing (the first dose of the study in TP1 cannot be missed, no more than 1 missed dose allowed per TP except Week 32 dose, no more than 2 missed doses allowed in TP1 through TP4 except Week 32 dose, participants can only miss or have an incomplete dose for either the first or second dose in TP4 (but not both), and the study doses on Weeks 26, 28, and 30 cannot be missed or incomplete). During the conduct of the study, it is possible that other deviations will be identified that can impact PK assessments, which can result in additional deviations to those noted above.

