### 5.3. Methods to Manage Missing Data

In general, no missing data will be imputed. For PK data, the following rules apply.

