#### 5.3.1. Concentrations below the limit of quantification

In all data presentations (except listings), concentrations below the limit of quantification (BLQ) will be set to zero. In the listings BLQ values will be reported as “<LLQ”, where LLQ will be replaced with the value for the lower limit of quantification.

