#### 5.3.2. Deviations, missing concentrations and anomalous values

In summary tables and plots of mean profiles of PK, statistics will be calculated having set concentrations to missing if 1 of the following cases is true:

1. A concentration has been collected as ND (ie, not done) or NS (ie, no sample);
2. A deviation in sampling time is of sufficient concern or a concentration has been flagged anomalous by the PK analyst.

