## 6. ANALYSES AND SUMMARIES

### 6.1. Primary Endpoint(s)

#### 6.1.1. $C_{\max}$ and $AUC_{\tau}$

The serum concentrations between Week 30 and Week 32 will be analyzed for the PK population using standard non-compartmental analysis to estimate the PK parameters ( $C_{\max}$ ,  $AUC_{\tau}$ ,  $T_{\max}$ ,  $C_{\text{av}}$ , and  $CL/F$ ) for each individual participant.

$C_{\max}$  and  $AUC_{\tau}$  are the primary endpoints. The primary analysis for  $C_{\max}$ , and  $AUC_{\tau}$  will be ANOVA with terms for treatment and randomization stratification factor (body weight categories) to compare switching arm and non-switching arm in log-transformed data in PK population. The mean difference and the confidence intervals (CI) for the differences will be obtained using ANOVA model. The mean differences and the CI will be exponentiated to provide estimates of geometric mean ratio (GMR) and the 90% confidence intervals for the ratio. Interchangeability will be established statistically if the 90% CI for the GMR is within 80.00% to 125.00% for both endpoints.

$C_{\max}$  and  $AUC_{\tau}$  will also be summarized descriptively for switching arm and non-switching arm. In addition, the primary endpoints will be summarized by ADA and NAb status at week 30.

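### Does the missing rule for concentrations below the limit of quantification leave the PK population and the primary log-scale ANOVA undefined?

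*SAP*

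**What the plan says.** Protocol 9.4 hands the SAP the task of describing "procedures for accounting for missing, unused, and spurious data". SAP 5.3 opens its answer with "In general, no missing data will be imputed. For PK data, the following rules apply". Two rules follow.

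- SAP 5.3.1: "In all data presentations (except listings), concentrations below the limit of quantification (BLQ) will be set to zero".
- SAP 5.3.2: "In summary tables and plots of mean profiles of PK, statistics will be calculated having set concentrations to missing". Its cases are samples not done or not available, sampling-time deviations of concern, and values flagged as anomalous. BLQ is not among them.

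For the primary endpoints, SAP 6.1.1 derives Cmax and AUCtau "using standard non-compartmental analysis to estimate the PK parameters". It then fits an ANOVA with treatment and weight-stratum terms "to compare switching arm and non-switching arm in log-transformed data in PK population".

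On membership, SAP 4 (like Protocol 9.3) requires participants to "have at least 1 primary endpoint" and excludes those whose missed samples materially affect the parameters. SAP 4 adds the timing sentence "The determination of PK population independent of the PK test results will be finalized prior to the releasing of the study database". None of this text mentions BLQ.

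**The concern.** Take a participant who received the Week 26, 28 and 30 doses in full, gave every sample, and had no measurable drug in any of them. The missed-sample exclusion does not apply. If an all-BLQ profile yields no Cmax or AUCtau, the endpoint criterion removes the participant. If membership is settled without reference to PK results, dosing and sampling records keep the participant in. SAP 4 can then seem to give two answers.

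Carrying the presentation rule into the analysis gives Cmax = AUCtau = 0, which has no logarithm. In an open-label trial, an unwritten rule that can be settled only once concentrations are known invites the question of whether the choice could tilt the result. The participant is also clinically informative: SAP 6.1.1, 6.2.1 and 6.2.2 plan to look at PK by ADA and NAb status, and a fully dosed participant with no measurable drug bears directly on that. Partly BLQ profiles can be log-transformed, but their AUCtau depends on a convention that is not stated.

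**Working it through.** **1. The plan's own figure.** Inputs from Protocol 9.2: GMR 1.05, CV 55%, correlation 0.5, 314 evaluable (157 per arm), limits 0.80 to 1.25.

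- Log-scale SD = sqrt(ln(1 + 0.55²)) = 0.5141.
- SE of the log GMR = 0.5141 × sqrt(2/157) = 0.0580.
- Single-endpoint power = Φ(ln(1.25/1.05)/0.0580 − 1.645) + Φ(ln(1.05/0.80)/0.0580 − 1.645) − 1 = 91.2% (91.1% with the t distribution).
- Both endpoints, correlation 0.5: 85.05% (84.9% with t), against 85% stated.
- 314/0.75 = 418.7, against about 420 stated.

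The sample size reproduces, so nothing in this point touches it.

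**2. Is there a contradiction in SAP 4?** The sentence after the timing sentence refers, in the same construction, to protocol deviations that are independent of PK test results. There the phrase restricts which deviations are meant. Read alike, the timing sentence fixes the result-independent part of the population before release, and the endpoint criterion applies as written. If instead a zero is counted as an observed Cmax, both statements put the participant in. The two collide only if the timing sentence is taken to cover the whole determination and a zero is taken not to be an endpoint. The text is silent on BLQ, not contradictory.

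**3. What each reading does to the primary analysis.** Let k participants have all-BLQ profiles.

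| Reading | In PK population | Log value | In ANOVA |
|---|---|---|---|
| No endpoint, so excluded | No | – | No |
| Included | Yes | None, since ln(0) is undefined and SAP 5.3 does not impute | No |

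The ANOVA set is the same either way. Illustration with four such profiles, all in the switching arm, and GMR 1.00 in the rest: 153 and 157 participants, SE = 0.5141 × sqrt(1/153 + 1/157) = 0.0584, 90% CI 0.908 to 1.101 under both readings. A choice made after the results are known therefore cannot move the GMR.

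The power cost of losing such participants is also the same under both readings. With 5, 10 or 15 lost from one arm, joint power (t version) is 84.3%, 83.6% or 82.8%, against 84.9%.

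**4. Partly BLQ profiles.** One quantifiable sample is enough for a Cmax, and that Cmax does not depend on the BLQ convention. For AUCtau, apply the linear trapezoid at 0, 48, 72, 96, 144, 240 and 336 h, with the listed samples exactly at the quantification limit (LLQ) and the others BLQ. Half the limit is used only as a contrast; it appears nowhere in the SAP. Units are LLQ × h.

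| Quantifiable samples | BLQ = 0 | BLQ = LLQ/2 | Ratio | Shift in GMR per participant, ln(ratio)/157 |
|---|---|---|---|---|
| 48 h only | 24 + 12 = 36 | 36 + 18 + 132 = 186 | 5.2 | 1.05% |
| 48 to 144 h | 168 | 252 | 1.5 | 0.26% |
| 48 to 240 h | 264 | 300 | 1.14 | 0.08% |

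The same convention would apply in both arms, so only an imbalance between arms moves the GMR at all.

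**5. What writing the rule down would add.** The addition considered is a stated zero convention, a statement on membership, and a count by arm of the participants left out. The first two leave the GMR where step 3 puts it. The count is descriptive: with 157 per arm, 5 against 0 gives a two-sided Fisher p of 0.06 and 6 against 0 gives 0.03. Placing all-BLQ participants in the PK population would also need further rules for CL/F (dose divided by zero) and Tmax, which are summarised on the same set.

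**The case for a change.** The strongest case for a change is that handling of such profiles can matter a great deal. Had they been kept at a small positive value, the conclusion could flip. With four in the switching arm at 2% of typical exposure and GMR 1.00 elsewhere, ln GMR = 4 × ln(0.02)/157 = −0.0997, so the GMR is 0.905 and the 90% CI 0.799 to 1.026, which fails. With five per arm kept at 1/10, 1/50 or 1/100 of the typical value and a true GMR of 1.05 in the others, simulated joint power is about 73%, 43% or 23%. A few sentences in the SAP would cost almost nothing.

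The arithmetic is right, but it measures a choice that the plan does not leave open. No substitution appears in the documents, SAP 5.3 rules out imputation in general, and neither reading of SAP 4 keeps such a profile at a positive value.

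Two parts of the objection stand. The only BLQ rule is worded for presentations, so the convention in the non-compartmental analysis is inferred from the SAP 5.3 introduction and from standard practice. And the GMR describes only participants with measurable drug. Writing the rule down would not alter that second limitation. Nor are these participants hidden: SAP 6.2.1 summarises and plots Ctrough by visit and by ADA and NAb status in the Safety-Randomized population, where BLQ values count as zero.

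**Conclusion.** No change follows. The SAP omits a detail: it does not say whether an all-BLQ profile counts as having a primary endpoint, and it gives no BLQ convention for the non-compartmental analysis. It does not contradict itself. Under either reading the participant is absent from the log-scale ANOVA, so the effect on the primary GMR, its 90% CI and the interchangeability decision is zero. What differs is the N of descriptive PK displays. For partly BLQ profiles the choice of convention is worth 0.08% to 1.05% of the AUCtau GMR per affected participant in the layouts checked, and nothing for Cmax.

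This rests on the SAP's no-imputation rule being followed, on 157 per arm with CV 55%, and on ignoring the weight strata. The documents give no LLQ and no BLQ frequency, so how often such profiles occur cannot be judged. Analysts would ordinarily carry the stated zero into the non-compartmental analysis and treat a zero parameter as not estimable on the log scale. Writing that down would record what they would do anyway.

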## 5. GENERAL METHODOLOGY AND CONVENTIONS

### 5.1. Hypotheses and Decision Rules

null hypothesis:  $H01 \quad \frac{\mu_s}{\mu_{ns}} < 0.8$                       or  $H02 \quad \frac{\mu_s}{\mu_{ns}} > 1.25$

alternative hypothesis:  $H_a \quad 0.8 \leq \frac{\mu_s}{\mu_{ns}} \leq 1.25$

$\mu_s$ : geometric mean for the switching arm

$\mu_{ns}$ : geometric mean for the non- switching arm

Interchangeability will be established statistically if the 90% CI for the GMR is within 80.00% to 125.00% for both  $C_{max}$  and  $AUC_{\tau}$ .

### 5.2. General Methods

The analyses for TP1 (lead-in period) will be performed for Humira group. The analyses for TP2 and beyond will be performed by treatment groups (switching arm vs non-switching arm).

#### 5.2.1. Analyses of Variance (ANOVA)

ANOVA will be used for comparing switching arm vs non-switching arm for  $C_{max}$  and  $AUC_{\tau}$ . GMR and the associated 90% 2-sided CI are will be obtained using analysis of ANOVA applied to log-transformed data, with terms for treatment and randomization stratification factor (body weight categories).

### 5.3. Methods to Manage Missing Data

In general, no missing data will be imputed. For PK data, the following rules apply.

#### 5.3.1. Concentrations below the limit of quantification

In all data presentations (except listings), concentrations below the limit of quantification (BLQ) will be set to zero. In the listings BLQ values will be reported as “<LLQ”, where LLQ will be replaced with the value for the lower limit of quantification.

#### 5.3.2. Deviations, missing concentrations and anomalous values

In summary tables and plots of mean profiles of PK, statistics will be calculated having set concentrations to missing if 1 of the following cases is true:

1. A concentration has been collected as ND (ie, not done) or NS (ie, no sample);
2. A deviation in sampling time is of sufficient concern or a concentration has been flagged anomalous by the PK analyst.

## 6. ANALYSES AND SUMMARIES

### 6.1. Primary Endpoint(s)

#### 6.1.1. $C_{\max}$ and $AUC_{\tau}$

The serum concentrations between Week 30 and Week 32 will be analyzed for the PK population using standard non-compartmental analysis to estimate the PK parameters ( $C_{\max}$ ,  $AUC_{\tau}$ ,  $T_{\max}$ ,  $C_{\text{av}}$ , and  $CL/F$ ) for each individual participant.

$C_{\max}$  and  $AUC_{\tau}$  are the primary endpoints. The primary analysis for  $C_{\max}$ , and  $AUC_{\tau}$  will be ANOVA with terms for treatment and randomization stratification factor (body weight categories) to compare switching arm and non-switching arm in log-transformed data in PK population. The mean difference and the confidence intervals (CI) for the differences will be obtained using ANOVA model. The mean differences and the CI will be exponentiated to provide estimates of geometric mean ratio (GMR) and the 90% confidence intervals for the ratio. Interchangeability will be established statistically if the 90% CI for the GMR is within 80.00% to 125.00% for both endpoints.

$C_{\max}$  and  $AUC_{\tau}$  will also be summarized descriptively for switching arm and non-switching arm. In addition, the primary endpoints will be summarized by ADA and NAb status at week 30.

### 6.2. Secondary Endpoint(s)

#### 6.2.1. Other PK endpoints

Secondary PK parameters ( $T_{\max}$ ,  $C_{\text{av}}$  and  $CL/F$ ) and serum concentrations collected between Week 30 and Week 32 will be summarized descriptively for switching arm and non-switching arm using PK population.  $C_{\text{trough}}$  collected in TP1 through TP4 will summarize descriptively by each visit using Safety-Randomized population for switching and non-switching arm.

For serum concentration during week 30 to week 32, mean concentration time plot, median concentration time plots and individual concentration time plots on both linear and semi-log scales will be provided for PK population by switching and non-switching arms. For  $C_{\text{trough}}$ , box plots will be provided using Safety-Randomized population by switching and non-switching arm for data collected in TP1 through TP4.

In addition, the summarization for secondary PK parameters ( $T_{\max}$ ,  $C_{\text{av}}$  and  $CL/F$ ), serum concentrations collected between Week 30 and Week 32 will be provided by ADA and NAb status at week 30. The plots for serum concentration during week 30 to week 32 will be provided by ADA and NAb status at week 30.  $C_{\text{trough}}$  at each visit will also be summarized and plotted by ADA and NAb status at the corresponding visit.

#### 6.2.2. Anti-drug antibody (ADA) and Neutralizing Anti-Drug Antibody (NAb) Results

For the ADA and NAb data, the percentage of participants with positive ADA and NAb will be calculated and summarized for the Safety-Randomized population by each visit for TP1 through TP4. The magnitude (titer) and time of first positive sample will also be described.

ADA and NAb status at the end of study will be used to characterize the participants response as either persistent or transient. For participants with at least one ADA/NAb positive sample, persistent response is defined as ADA/NAb positive at the last sample, and transient response is defined as having had at least one ADA/NAb positive sample, and an ADA/NAb negative at last sample.

In addition, the impact of ADA and NAb on PK over time will be assessed as specified in section 6.1.1 and 6.2.1.

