#### 4.2. Scientific Rationale for Study Design

This study design is consistent with recommendations outlined in the FDA Interchangeability guidance and FDA Clinical Pharmacology guidance 2016. These recommendations include lead-in period, switching and non-switching treatment arms, for which the switching arm should have at least 3 switches between the biosimilar and reference products. Furthermore, the duration of each treatment period should be sufficient to establish PK steady state, with PK samples collected at the end of the last treatment period in both treatment arms for determination of steady state PK parameters. PK parameters should be analyzed using a standard bioequivalence (BE) approach with acceptance margins of 80.00% to 125.00%.

Specific details regarding statistical approaches to data analysis for this study are discussed further in [Section 9](#).

This study is also designed to evaluate safety and immunogenicity after several investigational product switches between the switching and non-switching arms.

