## 2.2. Study Design

[figure not shown]
This is an open-label, multi-national, 2-arm, randomized, parallel-group study designed to evaluate the interchangeability of the switching arm (PF-06410293 and Humira), compared to non-switching arm (Humira), in participants with moderately to severely active RA on background methotrexate (MTX). For purposes of this protocol, the treatment arm that includes switches between PF-06410293 and Humira will be referred to as the “switching” arm, while the treatment arm that comprises continuous Humira treatment will be referred to as the “non-switching” arm.

This study will enroll a maximum of approximately 420 participants so that approximately 314 evaluable participants complete the study.

Study treatment will be provided through 4 treatment periods. For the first 10 weeks, all participants will receive Humira [Treatment Period (TP) 1]. Upon completion of TP1, participants will be randomized (1:1 ratio) into either the switching or non-switching arm prior to dosing on Week 10. Randomization will be stratified by 3 body weight groups (Week 10 weight) ( $\geq 40$  kg to  $< 70$  kg;  $\geq 70$  kg to  $< 100$  kg;  $\geq 100$  kg to  $\leq 130$  kg). Participants randomized to the non-switching arm will continue on Humira for the remainder of the study, and participants randomized to the switching arm will continue switching in each TP (TP2: PF-06410293; TP3: Humira; TP4: PF-06410293).

- Treatment Period 1 (Lead In Period) will begin with the first dose of investigational product on Week 0 (Day 1) and conclude with the completion of Week 10 pre-dose assessments.
- Treatment Period 2 will begin with the 1:1 randomization of the participants to either the switching arm or the non-switching arm at Week 10. Investigational product dosing for Week 10 will begin after the randomization process in the respective treatment arms and will conclude with the completion of Week 16 pre-dose assessments.
- Treatment Period 3 will begin with investigational product dosing on Week 16, and conclude with the completion of Week 22 pre-dose assessments.
- Treatment Period 4 will begin with investigational product dosing on Week 22 and continue through Week 30, where onsite investigational product dosing is scheduled at Weeks 22, 24, 26, 28, and 30, followed by a 2-week PK sampling period from Week 30 to Week 32. TP4 will conclude with end of treatment (EoT) assessments and final dose administration at Week 32.

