#### 3.2. Secondary Endpoint(s)

The secondary endpoints are

- Other serum adalimumab PK parameters and serum concentration, including  $T_{max}$ ,  $C_{av}$ , and  $CL/F$  obtained during the intensive PK sampling interval and  $C_{trough}$  obtained at scheduled PK sample timepoints.
- Safety endpoints including adverse events (AEs), laboratory test and vital signs. More detailed information is provided in Section 3.5.
- ADA and NAb endpoints including percent of participants with ADA/NAb and ADA/NAb titers over time.

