### 3.4. Baseline Value

For the TP1 summary, the baseline value is defined as the most recent measurement prior to the first dose of investigational product in TP1. For the TP2 to TP4 summary, the baseline value is defined as the most recent measurement prior to the first dose of investigational product after randomization in TP2.

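### SAP 6.2.2 does not separate ADA/NAb already present at Week 10, on Humira alone, from antibodies that arise after randomisation

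*SAP*

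**What the plan says.** **Design.** SAP 2.2: "For the first 10 weeks, all participants will receive Humira"; then "participants will be randomized (1:1 ratio) into either the switching or non-switching arm prior to dosing on Week 10". The Protocol's Schedule of Activities places ADA/NAb samples at Day 1 and Week 10, and again at Weeks 16, 22, 24, 26, 28, 30 and 32, each before dosing.

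**Purpose.** Immunogenicity in the two arms is a secondary objective. Protocol 4.2 puts it this way: "This study is also designed to evaluate safety and immunogenicity after several investigational product switches between the switching and non-switching arms".

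**Endpoint and population.** SAP 3.2 lists "ADA and NAb endpoints including percent of participants with ADA/NAb and ADA/NAb titers over time". The analysis set in SAP 4 is "All participants who are randomized and receive at least one dose of investigational product following the randomization at Study Week 10", whatever their antibody status at Week 10.

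**Analysis.** SAP 6.2.2: "the percentage of participants with positive ADA and NAb will be calculated and summarized for the Safety-Randomized population by each visit for TP1 through TP4". It also describes titre and the time of the first positive sample. Anyone with at least one positive sample is classed as persistent or transient according to the last sample.

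**Baseline.** SAP 3.4 says that for TP2 to TP4 summaries "the baseline value is defined as the most recent measurement prior to the first dose of investigational product after randomization in TP2". SAP 3.5.1 likewise counts TP2 to TP4 treatment-emergent adverse events only from that dose. SAP 6.6.1.2.1 splits immunogenic adverse effects by ADA status in TP1. Section 6.2.2 uses neither the baseline nor the split.

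**The concern.** By the Week 10 sample every participant is scheduled to have had five Humira doses (Weeks 0, 2, 4, 6 and 8) and no PF-06410293. An antibody found in that sample or earlier cannot be due to switching. It still counts as positive in both arms at each later visit for as long as it persists.

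The other summaries in 6.2.2 share the gap. The first positive sample may fall in TP1. A switching-arm participant positive only at Week 10 and negative at the last sample is reported as a transient responder in that arm, although the response came before any switch.

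Two questions bear directly on switching: do Week 10 negatives become positive more often, and do Week 10 positives have their titre boosted? Neither has a defined participant-level summary with its own denominator. A measure that draws the arms together also deserves a sharper companion here, because similar arms are the favourable result in an interchangeability study.

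**Working it through.** **The plan's own figures.** The documents state no rate, margin or power for ADA/NAb. The only sizing is for PK (Protocol 9.2): 314 evaluable of about 420 enrolled, 85% power. A simulation of the two co-primary equivalence tests with those inputs gives 84.9% at 157 per arm, and 314/0.75 = 419. Those figures stand, and this point does not touch them. They supply the arm sizes used below: 314/2 = 157, and 420/2 = 210 as an upper bound.

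**Formula.** At a given visit after Week 10, let
- b = share positive at Week 10, equal in expectation between arms because randomisation follows the lead-in;
- k = share of those still positive at the visit;
- i = share of Week 10 negatives who are positive at the visit.

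Prevalence in an arm is p = b·k + (1-b)·i. The arm difference (switching S minus non-switching N) is

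b·(k_S - k_N) + (1-b)·(i_S - i_N).

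If switching does not affect persistence, the first term is zero and the prevalence difference is (1-b) times the difference in new positivity.

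**Numbers (all assumed).** New positivity i = 15% non-switching and 25% switching: difference 10 points, ratio 25/15 = 1.67. Week 10 positives all stay positive (k = 1).

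| b | Prevalence, non-switching | Prevalence, switching | Difference | Ratio |
|---|---|---|---|---|
| 10% | 0.10 + 0.90×0.15 = 23.5% | 0.10 + 0.90×0.25 = 32.5% | 9 points | 1.38 |
| 30% | 0.30 + 0.70×0.15 = 40.5% | 0.30 + 0.70×0.25 = 47.5% | 7 points | 1.17 |
| 50% | 0.50 + 0.50×0.15 = 57.5% | 0.50 + 0.50×0.25 = 62.5% | 5 points | 1.09 |

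**Reversion.** Let 20% or 40% of Week 10 positives revert equally in both arms, with b = 30%. Prevalences become 34.5% vs 41.5%, or 28.5% vs 35.5%. The difference is still 7 points and the ratio is 1.20 or 1.25, still well below 1.67.

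**Subtracting the Week 10 rate.** With b = 30% and 20% reversion, the non-switching arm moves from 30% to 34.5%, a net rise of 4.5 points. New positives are 0.70×15% = 10.5 points and reversions 0.30×20% = 6 points; the net figure mixes the two. Net rises of 4.5 and 11.5 points still differ by 7, so subtraction does not undo the attenuation.

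**Precision with the smaller denominator.** The 95% half-width for a difference is 1.96·√[(p_N(1-p_N) + p_S(1-p_S))/n], with n per arm for prevalence. For new positivity, i replaces p and n(1-b) replaces n. At n = 157:

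| b | Week 10 negatives per arm | Prevalence difference | New-positivity difference |
|---|---|---|---|
| 10% | about 141 | 9 ± 9.9 | 10 ± 9.3 |
| 30% | about 110 | 7 ± 11.0 | 10 ± 10.5 |
| 50% | about 79 | 5 ± 10.8 | 10 ± 12.4 |

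At n = 210 and b = 30% the half-widths are 9.5 and 9.1. In these cases the restricted measure costs little precision up to b = 30% and somewhat more at 50%.

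**The case against.** Much can be said for the plan as written.

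- **Prevalence is not the only summary.** Persistent or transient status is a participant-level classification. A first positive at Week 16 or later is a post-randomisation onset, so time of first positive sample lets a reader partly recover new onsets.
- **The Week 10 level is displayed.** The table covers TP1 through TP4 in the same participants. With b in view, a reader could divide by (1-b), for example 7/0.70 = 10, provided persistence is equal in the arms.
- **TP1 status is used elsewhere.** SAP 6.6.1.2.1 separates TP1-positive and TP1-negative participants for immunogenic adverse effects.
- **Prevalence is a valid comparison of everyone randomised.** It captures any effect of switching on persistence (the b·(k_S - k_N) term), which new positivity among Week 10 negatives leaves out.
- **The endpoint is descriptive.** It has no test, margin or power.

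All of this stands. It narrows the gap without closing it: no post-randomisation incidence with a Week 10-negative denominator is specified, and by-visit titre summaries cannot show a boost within a participant.

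A reader might go further and infer that 6.2.2 contradicts SAP 3.4. It does not: 3.4 governs TP2 to TP4 summaries, and the ADA/NAb table is defined over TP1 to TP4. A reader might also infer that new onset is wholly invisible in the planned output; the time of first positive sample shows otherwise.

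**Conclusion.** The point holds as a worthwhile, inexpensive improvement, to be considered rather than required. Section 6.2.2 mixes antibodies formed on Humira before randomisation with those formed after it, so its by-visit rates give a diluted view of new positivity after switching.

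The size is unknown because the documents give no ADA or NAb rate. The attenuation factor is (1-b), which assumes that switching does not alter persistence in Week 10 positives. It is negligible if b is near 0; a 10-point difference becomes 9, 7 or 5 points at an assumed b of 10%, 30% or 50%. The 15% and 25% rates are also assumptions.

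Two stronger conclusions might be drawn, and the documents support neither. The arms are not biased by imbalance, since randomisation follows the lead-in and b is equal in expectation. The interchangeability conclusion is not at risk from this either: SAP 5.1 rests it on the C_max and AUC_τ confidence intervals alone.

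**What to change.** Before database release, add to SAP 6.2.2, by arm and using the SAP 3.4 baseline for TP2 to TP4:

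1. Among participants negative at Week 10, the proportion newly ADA-positive, and separately newly NAb-positive, at any sample after the first randomised dose. Give the arm difference with a 95% CI, and measure time to first positive from Week 10.
2. Among participants positive at Week 10, the proportion whose titre later rises above a threshold set in advance from the validated assay. The documents give no dilution scheme, so the value must come from the assay documentation.

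Report both alongside the by-visit prevalence, which should stay because it also reflects persistence.

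The cost is some SAP wording and two tables, from samples already scheduled. The drawback is the smaller denominator: with 157 per arm, about 141, 110 or 79 Week 10 negatives at b = 10%, 30% or 50%.
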